9.1.4 Vital Signs

Body temperature, blood pressure, pulse and respirations will be recorded on admission and at least every 4 hours thereafter while the patient is in the ICU.

9.1.5 Oximetry

Oximetry will be measured on room air on admission.

9.1.6 Other Clinical Procedures

All patients will have, in addition to standard labs, additional labs drawn for thromboelastography, platelet function determination, and coagulation factor levels, on admission, after each 6 units of whole blood or PRBCs transfused, at 3 and 6 hours of resuscitation, at the time of hemostasis, and on ICU days 1,3 and 5. Tests for hemolysis will be performed along with regular clinical labs on ICU day 1. These labs will be drawn during clinical lab collection so no extra needle stick is required.

PI: [name]

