5 CRITERIA FOR EVALUATION

5.1 Primary Efficacy Endpoint

The primary objective is to assess the clinical efficacy of whole blood compared to component therapy for trauma patients requiring massive transfusion. Primary analysis will compare volume of blood transfusion within 24 hours of admission for patients without severe TBI (defined as GCS \leq 8 and imaging evidence of brain injury) for patients who received WB versus component therapy for initial resuscitation.

Secondary Efficacy Endpoints

The secondary objectives will evaluate the effect on survival; the development of multiple complications related to survival; and wastage data. The full list of secondary endpoints is as follows:

1. Volume of blood transfusion within 24 hours of admission for patients with severe TBI (GCS \leq 8 and imaging evidence of brain injury) and for entire cohort of patients.
2. Thromboelastography parameters including maximum amplitude, reaction time, alpha angle, fibrinolysis, and platelet function at 3 and 6 hours of resuscitation, after every 6 units of whole blood equivalent (WB or PRBCs) given, at the time of completion of resuscitation (time of last unit of blood product given), and on ICU days 1, 3 and 5.
3. 30-day mortality;

PI: [name]

4. Duration of need for renal replacement therapy, mechanical ventilation, ICU admission, and hospital stay;
5. Number of units of blood products transfused by component/product during first 24 hours of admission and total hospitalization;
6. Complications which include clinical coagulopathy, infection, venous thromboembolism, cerebrovascular accident, acute coronary syndrome, transfusion-related lung injury, transfusion-associated cardiac overload during total hospitalization;
7. Hemolysis as measured by haptoglobin, bilirubin, lactate dehydrogenase, and direct antiglobulin on ICU day 1;
8. Wastage of blood units

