8 STUDY TREATMENTS

8.1 Method of Assigning Patients to Treatment Groups

Treatment groups are not assigned as this is an observational study. Treatment is determined by the eligibility of the patient (male or female) and the availability of whole blood when the patient presents. Adult male patients meeting eligibility who have

PI: [name]

received or will receive whole blood for traumatic resuscitation will be enrolled in the whole blood group. Enrollment of 49 patients receiving whole blood is planned. Adult male patients meeting eligibility criteria who present when whole blood is not available will receive component therapy and will be enrolled in the component therapy group. Enrollment of 49 control (component therapy group) patients is planned. Female patients meeting eligibility criteria will also be included in the component therapy group (see Section 6.1, Study Population, for rationale).

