10 EVALUATIONS BY VISIT

10.1 Visit 1 (Days 1-365)

Hospital Stay visit: typically 1-14 days, but can be as long as one year.

1. Assign the patient a unique study number. This number is planned to be listed on a bracelet in a packet present in the ED. The bracelet will be placed on the patient's wrist during initial admission procedures to identify the patient as a participant in the study.
2. All demographic data, past medical history, and concurrent medications are recorded by hospital staff as part of standard admission procedures. This information will be reviewed by study personnel during analysis.
3. Physical examination, vital signs, and standard clinical labs are performed and recorded by hospital staff.
4. Additional blood samples will be collected for TEG/platelet mapping and CAT (one 4 mL sodium citrate and one 4 mL heparinized tube per draw). This will be performed at the following time points: on admission, after each 6 units of whole blood equivalent (WB or PRBCs) transfused, at 3 and 6 hours of resuscitation, at the time of hemostasis determined by the trauma surgeon, and on ICU days 1,3 and 5.
5. Standard clinical labs including complete blood counts (white blood cell count, hemoglobin, hematocrit, and platelet count), blood chemistries, and standard coagulation labs (prothrombin time, international normalized ratio, partial thromboplastin time) will be performed at least daily as standard of care. This data will also be collected as part of the study. Of note, serial platelet counts obtained

PI: [name]

as standard of care will be monitored no less frequently than daily at noon (see also Schedule of Events).

6. In addition to standard clinical labs, hemolysis labs will be performed as listed above on ICU day 1 which will be billed to the study.
7. Follow up by chart review will continue for the duration of the hospital stay (typically roughly 14 days but can be up to one year).
8. Chart review during the hospital stay will collect the following data:

Data collected on initial 24 hours of hospital stay:

Medical record number

Date of birth /age

Sex

Race

Weight

Height

Injury date/time

Arrival date/time

Emergency Department exit date/time

Operating room arrival time

Tier (defines levels of critical condition for trauma patients)

Injury description

Mechanism of injury

Injury Severity Score

Glasgow Coma Scale and vitals

Intubation status and location of intubation

Whether patient received cardiopulmonary resuscitation

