15 STATISTICAL METHODS AND CONSIDERATIONS

Prior to the analysis of the final study data, a detailed Statistical Analysis Plan (SAP) will be written describing all analyses that will be performed. The SAP will contain any modifications to the analysis plan described in this protocol.

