15.4 Analysis of Secondary Endpoints

Continuous variables and categorical variables will be analyzed as described above (section 15.3). Mixed effects linear regression models will be used to evaluate coagulopathy over time and to adjust for confounding variables.

To analyze coagulopathy over time we will use a mixed effects linear regression model. A mixed effects linear regression model will also be used to adjust for confounding variables such as sex, age, comorbidities, severity of injury, and physiologic parameters of shock including pH and temperature, and use of a rapid transfuser (which more effectively warms blood).

Quarterly safety monitoring will compare categorical variables including mortality and development of complications (duration of need for renal replacement therapy,

PI: [name]

mechanical ventilation, ICU admission, and hospital stay; clinical coagulopathy, infection, venous thromboembolism, cerebrovascular accident, acute coronary syndrome, transfusion-related lung injury, transfusion-associated cardiac overload; transfusion reactions including clinical transfusion reactions and rates of hemolysis as measured by haptoglobin, bilirubin, lactate dehydrogenase, and direct antiglobulin). Categorical variables will be compared using the chi-squared test.

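### Admission TEG is collected but named neither in the TEG endpoint time points nor among the mixed-model covariates of a non-randomised comparison

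*Protocol*

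**What the plan says.** **Sampling.** Protocol section 9.1.6 schedules TEG in all patients "on admission, after each 6 units of whole blood or PRBCs transfused, at 3 and 6 hours of resuscitation", and later at hemostasis and on ICU days 1, 3 and 5. Section 10.1 repeats the admission draw: "This will be performed at the following time points: on admission, after each 6 units of whole blood equivalent (WB or PRBCs) transfused".

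**Endpoint.** The second secondary efficacy endpoint in section 5.1 lists TEG parameters "at 3 and 6 hours of resuscitation, after every 6 units of whole blood equivalent (WB or PRBCs) given", then at completion of resuscitation and on ICU days 1, 3 and 5. Admission is not in the list. The synopsis gives the same time points.

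**Model.** Section 15.4: "To analyze coagulopathy over time we will use a mixed effects linear regression model". The next sentence says that a mixed model will also "adjust for confounding variables such as sex, age, comorbidities, severity of injury, and physiologic parameters of shock including pH and temperature", and adds use of a rapid transfuser. Neither sentence mentions admission TEG, change from admission, or a group-by-time contrast.

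**Allocation.** Section 8.1: "Treatment is determined by the eligibility of the patient (male or female) and the availability of whole blood when the patient presents". The whole blood group is all male. Prospective controls are women, plus men who arrive when whole blood is out of stock.

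**The concern.** Functional coagulopathy by TEG is the first secondary objective in section 3.2. In a non-randomised comparison of a repeated laboratory measure, the pre-treatment value of that measure is the natural baseline. This protocol collects it, and names pH, temperature and injury severity for adjustment, but gives the admission value itself no role.

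Two things are at stake. An arrival difference between groups that the named covariates do not capture could appear in the later TEG values as if it were an effect of the product. And if admission TEG predicts later TEG, leaving it out makes the standard error larger than it needs to be.

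**Working it through.** **1. The plan's own figures.** The plan gives no figure for TEG. Its sizing concerns the primary endpoint: 49 − 18 = 31 per group, which reproduces. The stated 80% power cannot be checked, because no effect size or SD is given. With two-sided 0.05 it implies a standardised difference of (1.960 + 0.842) × √(2/31) = 0.71. Nothing below rests on this.

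**2. Places compared.**

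| Place in protocol | Is admission TEG there? |
|---|---|
| 9.1.6 and 10.1, sampling | Yes |
| Synopsis and 5.1, endpoint time points | No |
| Synopsis and 15.4, named covariates | No, but the list is open |
| 15.4, form of the model over time | Not stated |

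**3. Precision.** Let r be the within-group correlation between admission and one follow-up value. It is not in the documents; 0.3 to 0.7 is assumed. With admission TEG as a covariate, and no other covariates, residual variance is multiplied by 1 − r², which is equivalent to 1/(1 − r²) times the patients.

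| r | 1 − r² | Reduction | 1/(1 − r²) | Equivalent extra patients |
|---|---|---|---|---|
| 0.3 | 0.91 | 9% | 1.10 | 10% |
| 0.5 | 0.75 | 25% | 1.33 | 33% |
| 0.7 | 0.51 | 49% | 1.96 | 96% |

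These are upper limits. Injury severity, pH and temperature would already explain part of the same variance. If the arrival means differ by δ SD, the variance of the adjusted contrast also rises by a factor 1 + δ²/4; for δ = 0.5 that is 1.0625.

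**4. Bias (illustration).** Take a true effect of zero and an arrival difference of δ SD, assumed to be 0.2 to 0.5. With no baseline and no other covariates, the expected follow-up difference is r × δ, with standard error √(2/n). For n = 49 per group, √(2/49) = 0.202. Example: δ = 0.3 and r = 0.5 give 0.15 SD; 0.15/0.202 = 0.742; the two-sided 5% test then rejects with probability P(Z > 1.96 − 0.742) + P(Z < −1.96 − 0.742) = 11.5%.

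| δ | r = 0.3 | r = 0.5 | r = 0.7 |
|---|---|---|---|
| 0.2 | 0.06 SD, 6.0% | 0.10 SD, 7.9% | 0.14 SD, 10.7% |
| 0.3 | 0.09 SD, 7.3% | 0.15 SD, 11.5% | 0.21 SD, 18.0% |
| 0.5 | 0.15 SD, 11.5% | 0.25 SD, 23.6% | 0.35 SD, 41.0% |

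With n = 31 per group, the rejection rates run from 5.6% to 28.1%.

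A simulation of 4,000 runs (n = 49, one follow-up) agrees. For (δ, r) = (0.3, 0.5), (0.5, 0.5) and (0.5, 0.7), the unadjusted bias was 0.15, 0.25 and 0.35 SD, with false-positive rates of 10.9%, 22.0% and 41.0%. With admission TEG as a covariate, the bias was within 0.004 SD of zero and the rates were 4.9%, 5.4% and 4.6%. The simulation lets all confounding act through admission TEG and omits the named covariates, so it shows the most that adjustment could do.

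**5. The two ways of using a baseline.** They are not interchangeable when arrival means differ. A group-by-time contrast with free arrival means compares changes. At one follow-up its variance is 2(1 − r) times that of the unadjusted comparison: 1.4, 1.0 and 0.6 for r = 0.3, 0.5 and 0.7. The gains in step 3 therefore belong to the covariate form. The two forms also assume different things about how an arrival gap would evolve without treatment: in step 4 it shrinks to r × δ, whereas the change contrast takes it to persist at δ.

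**The case against.** A reader might infer that the plan will not use admission TEG, and that arrival differences will therefore be read as treatment effect. The documents do not support that.

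- No section excludes admission TEG. The covariate list in 15.4 is introduced as examples, and it follows the sentence on coagulopathy over time without being tied to the TEG model.
- A mixed model over time could already carry the admission value as its first response, with the effect read from group-by-time.
- Section 15 says that "a detailed Statistical Analysis Plan (SAP) will be written describing all analyses that will be performed". Details of model form commonly belong there.
- Allocation follows sex and stock, not coagulation status. Sex is named for adjustment, as are injury severity, pH and temperature, and these would absorb part of an arrival difference. Nothing in the protocol links stock to arrival TEG among men.

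All of this stands, and it limits the point. It does not remove it: the protocol itself fixes the endpoint time points and names covariates, and both leave out a baseline that it collects. If admission entered only as one more response under an overall group effect, arrival differences would still reach the estimate, so its role has to be stated.

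The remedy also has limits. The synopsis admits component patients who have already received blood, and section 8.1 allows the same for whole blood, so some admission samples may follow the first unit. Conditioning on those could remove real effect. Some samples may be missing, and no section says that historical controls had TEG.

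**Conclusion.** The point holds as an omission worth correcting for a secondary endpoint. Admission TEG is scheduled in all prospective patients but is absent from the endpoint time points and the named covariates, in a comparison whose groups are formed by sex and blood stock.

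The gain in residual variance is at most 9%, 25% or 49% at one follow-up for assumed correlations of 0.3, 0.5 or 0.7. The bias that could be avoided is 0.06 to 0.35 SD if arrival differences are 0.2 to 0.5 SD and the named covariates capture none of them; to the extent that they do, it is smaller. The protocol gives neither the correlations nor the arrival differences, so these figures illustrate scale and do not predict this study's results. The primary comparison of transfusion volume by t-test or Wilcoxon test is unaffected.

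**What to change.** In section 15.4, state that the mixed model for each TEG parameter uses that parameter's admission value as its baseline. It can be a fixed covariate, or the time-zero response with the group-by-time term carrying the effect. Name one form as the main analysis before the data are seen: the covariate form gives the precision in step 3, and the response form keeps patients without an admission sample.

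Record whether each admission sample preceded the first unit of blood, and repeat the analysis restricted to pre-transfusion samples.

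Admission maximum amplitude may be added to the adjusted transfusion-volume model as a sensitivity analysis, in the prospective data sets only.

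The cost is small but not nil. No extra draw is needed. One timing item must be recorded, and patients without a usable pre-transfusion sample drop out of the covariate form and of the restricted analysis.

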9.1.7 Adverse Events

Information regarding occurrence of adverse events will be captured throughout the study. Duration (start and stop dates and times), severity/grade, outcome, treatment and relation to study drug will be recorded on the case report form (CRF).

Morbidity and mortality in this study population (patients requiring massive transfusion for trauma) is high.²⁹ Therefore we expect a relatively large number of adverse events, and resulting SAE reports, for reasons unrelated to the study.

9.2 Clinical Laboratory Measurements

9.2.1 Hematology

Patients will receive standard hematology tests including complete blood counts as standard of care no less than daily (see also Schedule of Events).

9.2.2 Blood Chemistry Profile

Patients will receive this no less than daily as standard of care.

9.2.3 Pregnancy Test

Female patients of childbearing age will receive this on admission or shortly thereafter as standard of care.

9.3 Research Laboratory Measurements

9.3.1 Thromboelastography (TEG)/platelet mapping

For TEG testing, 1 mL of patient blood sample will be added to a plastic vial containing kaolin. The vial will be capped securely and the contents will be mixed by gentle inversion. 340 microliters of the resultant mixture will be pipetted into a disposable TEG cup containing 20 microliters of calcium chloride preloaded in the TEG. To minimize any risk of splashing, personnel will use standard personal protective equipment. The cup will be raised into the TEG chamber and testing will begin. Platelet mapping assesses platelet function by repeating TEG parameters in the presence of platelet activators and inhibitors. After approximately 30 minutes, testing is complete. The TEG apparatus is completely enclosed. All syringes, pipettes, and cups used for this procedure will be placed in a biohazard container.

9.3.2 Calibrated Automated Thromboelastogram (CAT) testing

PI: [name]

For CAT testing, blood not used for TEG will be transferred to 5 mL plastic centrifuge tubes. The tubes will be capped securely and centrifuged. The resulting plasma will be transferred to plastic cryotubes, which are enclosed, and frozen until testing. All syringes, pipettes, and centrifuge tubes will be placed in a biohazard container. 80 microliters of thawed plasma will be pipetted to each well of a 96-well plate (less wells used for controls). The plate is then placed in the CAT for testing, which is enclosed. At the end of the CAT testing cycle, the plate and pipettes will be placed in a biohazard container. All transfers of potentially biohazardous material will take place in a biosafety cabinet to minimize the risk of splashes. At all times during laboratory testing, proper PPE will be worn and, at the end of each testing day, laboratory surfaces will be disinfected according to protocol.

10 EVALUATIONS BY VISIT

10.1 Visit 1 (Days 1-365)

Hospital Stay visit: typically 1-14 days, but can be as long as one year.

1. Assign the patient a unique study number. This number is planned to be listed on a bracelet in a packet present in the ED. The bracelet will be placed on the patient's wrist during initial admission procedures to identify the patient as a participant in the study.
2. All demographic data, past medical history, and concurrent medications are recorded by hospital staff as part of standard admission procedures. This information will be reviewed by study personnel during analysis.
3. Physical examination, vital signs, and standard clinical labs are performed and recorded by hospital staff.
4. Additional blood samples will be collected for TEG/platelet mapping and CAT (one 4 mL sodium citrate and one 4 mL heparinized tube per draw). This will be performed at the following time points: on admission, after each 6 units of whole blood equivalent (WB or PRBCs) transfused, at 3 and 6 hours of resuscitation, at the time of hemostasis determined by the trauma surgeon, and on ICU days 1,3 and 5.
5. Standard clinical labs including complete blood counts (white blood cell count, hemoglobin, hematocrit, and platelet count), blood chemistries, and standard coagulation labs (prothrombin time, international normalized ratio, partial thromboplastin time) will be performed at least daily as standard of care. This data will also be collected as part of the study. Of note, serial platelet counts obtained

PI: [name]

as standard of care will be monitored no less frequently than daily at noon (see also Schedule of Events).

6. In addition to standard clinical labs, hemolysis labs will be performed as listed above on ICU day 1 which will be billed to the study.
7. Follow up by chart review will continue for the duration of the hospital stay (typically roughly 14 days but can be up to one year).
8. Chart review during the hospital stay will collect the following data:

Data collected on initial 24 hours of hospital stay:

Medical record number

Date of birth /age

Sex

Race

Weight

Height

Injury date/time

Arrival date/time

Emergency Department exit date/time

Operating room arrival time

Tier (defines levels of critical condition for trauma patients)

Injury description

Mechanism of injury

Injury Severity Score

Glasgow Coma Scale and vitals

Intubation status and location of intubation

Whether patient received cardiopulmonary resuscitation

Total fluids received in the first 24 hours

Data collected on initial 5 days of hospitalization:

Vital signs: systolic and diastolic blood pressure, heart rate, respiratory rate, oxygen saturation, temperature

Hemoglobin

Hematocrit

PI: [name]

White blood cell count
Platelet count
Sodium
Potassium
Chloride
Bicarbonate
Blood urea nitrogen
Creatinine
Glucose
Aspartate transaminase (AST)
Alanine transaminase (ALT)
Total bilirubin
Direct bilirubin
Alkaline phosphatase
pH
Lactate
PaCO₂ (arterial CO₂ partial pressure)
PaO₂ (arterial oxygen partial pressure)
Base excess
Prothrombin time (PT)
INR
Partial thromboplastin time (PTT)
Fibrinogen
Thrombin
Antithrombin Complex
Factor V
Factor VII
Factor VIII
Factor X
D-dimer
Lactate dehydrogenase (LDH)

PI: [name]

Haptoglobin

Data collected on entire hospitalization:

Procedures performed during hospitalization

Operations performed during hospitalization

Discharge date

Disposition

Discharge capacity

Date and cause of death if applicable

Comorbidities

Admission medications

Total hospital and intensive care unit length of stay

Number of days on ventilator

Number of days on dialysis

Number of days on vasopressor medications

Number and nature of operative procedures

Development of venous thromboembolism

Development of acute kidney injury

Development of acute respiratory distress syndrome

Development of liver failure

Suspected or confirmed transfusion reaction

Hemolytic transfusion reaction

Transfusion associated lung injury

Development of cardiac failure

Development of clinical coagulopathy

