CONTROL PRODUCT, DOSE AND ROUTE OF ADMINISTRATION	Component therapy consisting of packed red blood cells, thawed fresh frozen plasma and platelets in a 1:1:1 ratio. Product will be transfused intravenously as needed to replace ongoing blood loss and restore/maintain hemodynamic stability and hemostasis.
DURATION OF PATIENT PARTICIPATION AND DURATION OF STUDY	
Patient participation includes up to 24 hours of transfusion, up to 5 days of laboratory testing, and up to one year of follow up by chart review. Follow up by chart review will continue throughout the patient's hospital stay or up to one year, whichever is shorter. Most hospital stays are anticipated to be approximately 14 days.
 
Screening: not applicable
 
Treatment: 1 day / 24 hours. Patients will receive whole blood only during initial resuscitation for traumatic hemorrhage, which is generally complete within a few hours.
 
Follow-up: 5 days (laboratory testing) + chart review for up to 1 year if the patient remains in the hospital
 
The total duration of study enrollment and completion of follow up is expected to be two years.

CONCOMITANT MEDICATIONS	Allowed: all Prohibited: none

EFFICACY EVALUATIONS:
	

PRIMARY ENDPOINT
	
1. Primary analysis will compare volume of blood transfusion within 24 hours of admission for patients with traumatic hemorrhagic shock without severe TBI (GCS \leq8 and evidence of brain injury on imaging) who have received WB versus component therapy for initial resuscitation.

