4 STUDY DESIGN

4.1 Study Overview

This is a single center, prospective cohort study. Enrollment of approximately 98 patients is planned, 49 receiving whole blood and 49 receiving component therapy. This is an observational study planned during initiation of a change in practice at our institution initially allowing up to 4 units of whole blood transfusion for adult male trauma patients. If initial patients receiving whole blood show no evidence of hemolysis and thrombocytopenia compared to patients receiving component therapy, up to 6 units of whole blood transfusion will be allowed (see below, and section 5.2, Safety Evaluations). Patients in the whole blood, or index, group are adult male trauma patients presenting in hemorrhagic shock (systolic blood pressure < 100) requiring massive transfusion activation who receive whole blood for resuscitation. Two control groups will be utilized. The prospective control group consists of adult male patients who present during times when whole blood is not available, as well as adult female patients, presenting in hemorrhagic shock (systolic blood pressure <100) requiring massive transfusion activation. Additionally, a second control group consisting of historical

PI: [name]

controls receiving component therapy will be analyzed (see Section 6, Patient Selection, for details of index and control groups).

All patients will have, in addition to standard labs, additional labs drawn for thromboelastography, platelet function determination, and coagulation factor levels (see Section 9.1.6, Other Clinical Procedures, for details of specific lab tests and timing).

Patients who meet all inclusion criteria and none of the exclusion criteria will be enrolled into the study.

Total duration of patient participation will be approximately 1 year (365 days), or the duration of the hospital stay, whichever is shorter. This includes up to 5 days of laboratory testing during initial resuscitation and subsequent admission, and up to one year of follow up via chart review if the patient remains in the hospital. Total duration of the study including recruitment and follow up is expected to be 2 years.

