11.2.1 Serious Adverse Experience Reporting

Study site will document all SAEs that occur (whether or not related to study drug) per [UCLA OHRPP Guidelines](#). The collection period for all SAEs will begin after admission and end after discharge.

In accordance with the standard operating procedures and policies of the Institutional Review Board, the site investigator will report SAEs to the IRB.

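### 30-day mortality is a secondary endpoint, but the text ends follow-up at discharge (about day 14 for most patients) and gives no way to learn day-30 status after an earlier discharge

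*Protocol*

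**What the plan says.** **Endpoint.** 30-day mortality is a secondary objective in the synopsis and in Section 3.2. It is also a secondary endpoint in the synopsis and in the list under Section 5.1 ("3. 30-day mortality").

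**Follow-up in the narrative text.**
- Synopsis, duration of participation: follow-up after the laboratory phase is "chart review for up to 1 year if the patient remains in the hospital", and "Most hospital stays are anticipated to be approximately 14 days".
- Section 4.1: "Total duration of patient participation will be approximately 1 year (365 days), or the duration of the hospital stay, whichever is shorter".
- Section 10.1: Visit 1 is described as "Hospital Stay visit: typically 1-14 days, but can be as long as one year", and item 7 reads "Follow up by chart review will continue for the duration of the hospital stay (typically roughly 14 days but can be up to one year".

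**Where deaths are recorded.** The chart-review list in Section 10.1 has "Date and cause of death if applicable" among the items for the whole hospitalization. Death is also an evaluated adverse event (Section 5.2) and an SAE outcome (Section 11.2). For SAEs, Section 11.2.1 says: "The collection period for all SAEs will begin after admission and end after discharge".

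**Looser statements.** The heading of Section 10.1 gives Visit 1 a range of days 1 to 365. The chart-review column of the Schedule of Events runs from day 0 to day 365, and the rows for clinical outcomes and adverse events appear to be marked in it. Section 9.1.7 has adverse events captured for as long as the study lasts.

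**The concern.** A 30-day mortality endpoint needs each patient's vital status on day 30. The protocol's follow-up rule supplies that only for patients who die in hospital by then or are still inpatients on day 30. A patient who leaves alive on day 14 passes out of planned observation with the endpoint undetermined.

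The result could therefore be in-hospital mortality under a 30-day label. The two differ in kind: with follow-up that stops at discharge, whether a later death is seen depends on when the patient went home. The groups are not randomised. Section 8.1 says that sex and the availability of whole blood decide the treatment, so discharge timing may differ between groups for reasons unrelated to the product. The same question arises for the historical controls if their mortality is compared.

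**Working it through.** The protocol states no figure for this endpoint, so there is none to reproduce. The check compares the endpoint's horizon with each stated observation window, then illustrates the scale under labelled assumptions.

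**Step 1. Windows side by side.**

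| Place | Window | Reaches day 30 after an earlier discharge? |
|---|---|---|
| Synopsis, 3.2, 5.1 (endpoint) | Day 30 | Required |
| Synopsis, duration | Hospital stay or one year, whichever is shorter | No |
| 4.1 | Same rule | No |
| 10.1, item 7 | Hospital stay | No |
| 10.1, date of death | Whole hospitalization | No |
| 11.2.1, SAEs | Ends after discharge, no day given | No |
| 10.1 heading; Schedule column | Up to day 365, as part of Visit 1 | Only if Visit 1 outlasts the stay, which 10.1 does not say |
| 9.1.7, adverse events | Throughout the study | No post-discharge method given |

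**Step 2. Is 30-day just loose wording for in-hospital?** No. Section 5.1 limits complications to the total hospitalization in the same list, so the protocol uses a hospital-stay window where it wants one.

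**Step 3. Shortfall for a typical survivor.** 30 − 14 = 16 days without planned observation.

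**Step 4. Illustration of how many patients are affected.** From the protocol: 49 patients per group. Assumed, because the protocol gives no such rates: 60% to 80% survive to discharge, and 50% to 95% of those leave before day 30.

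Patients without planned day-30 status = 49 × survival to discharge × share leaving before day 30.
- Low: 49 × 0.60 × 0.50 = 14.7 (30%)
- High: 49 × 0.80 × 0.95 = 37.2 (76%)

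Cross-check with an assumed exponential length of stay: a mean of 14 days gives 1 − exp(−30/14) = 0.88 leaving before day 30; a median of 14 days gives 1 − 2^(−30/14) = 0.77. With the same survival range, 0.60 × 0.77 = 46% (22.6 of 49) to 0.80 × 0.88 = 70% (34.5 of 49). Both lie inside the wider range.

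**Step 5. Illustration of deaths missed.** Assumed: 1% to 5% mortality between discharge and day 30.
- Low: 14.7 × 0.01 = 0.15 per group, or 0.3% of 49
- High: 37.24 × 0.05 = 1.86 per group, or 3.8% of 49

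The answer varies more than tenfold with the assumptions. It shows the order of size only.

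**The case against.** **The Schedule of Events runs to day 365.** With clinical outcomes and adverse events in that column, and adverse events captured throughout the study, one could say that post-discharge review was intended. This stands in part: the document is internally inconsistent about follow-up, not uniformly limited to discharge. It does not supply the endpoint. The column is labelled as Visit 1, Section 10.1 defines Visit 1 as the hospital stay, and the synopsis and Section 4.1 make the year conditional on remaining in hospital. No call, clinic visit, registry check or later record search is described.

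**Death is recorded in several places.** True: it is an adverse event and an SAE outcome as well as a chart-review item. None of these comes with a means of learning about a death after discharge.

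**The statistical analysis plan can deal with it.** It can say how patients discharged alive are counted, and that is properly its job. Date of death and discharge date are both collected, so in-hospital death by day 30 can be derived and early discharges identified. It cannot recover vital status that was never collected, and the follow-up window is fixed in the protocol.

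**Few deaths would be missed.** Probably so, and this limits the weight of the point.

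Two stronger readings are tempting. A reader might infer that in-hospital deaths will certainly be published as 30-day mortality. The protocol does not say that patients discharged alive are counted as day-30 survivors, so this is a possibility only. A reader might also infer a sizeable bias between the groups. The protocol gives no survival, discharge or late-mortality rates by group, so no between-group figure can be supported.

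**Conclusion.** The mismatch is real. The stated follow-up rule cannot produce the stated endpoint for patients who leave hospital alive before day 30, and the looser day ranges elsewhere do not cure this. The data as planned support in-hospital mortality.

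What the protocol itself establishes is that a typical stay of about 14 days falls 16 days short of the endpoint. The share of patients affected (30% to 76% per group) and the deaths missed (about 0.1 to 1.9 per group) rest wholly on assumed rates. The true number of missed deaths is unknown and probably small. The 24-hour primary endpoint and the sample size built on it are untouched. The point is to match the endpoint's label to the data collected. It is worth correcting, but it does not threaten the study.

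**What to change.** Choose one.

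**(a) Keep 30-day mortality and collect it.** Add a day-30 vital-status check, from record sources named in the protocol, for every patient discharged earlier. Apply it identically to both prospective groups, and to the historical controls if mortality is compared with them. Report patients not found as unknown, not as alive. Confirm that the consent and HIPAA waiver (Sections 9 and 17.3) covers the look-up. Amend the synopsis, Section 4.1, Section 10.1 and the Schedule of Events so that none still ends follow-up at discharge. Cost: one look-up per early discharge, about 29 to 74 across the two prospective groups under the assumptions above (2 × 14.7 = 29.4 to 2 × 37.24 = 74.5), plus historical controls if included, whose number the protocol does not state.

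**(b) Keep the follow-up and rename the endpoint.** In the synopsis, Section 3.2 and Section 5.1, redefine it as in-hospital mortality through day 30. Report discharge alive separately, and state that the measure depends on discharge timing. Align the day ranges in the Section 10.1 heading and the Schedule with the hospital-stay limit. Cost: wording in five places and no new data.

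Either option needs an IRB-approved amendment under Section 17.1. Neither changes patient care.
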